Signs and symptoms of OSD are often non-specific to the ocular surface and caused by allergic, pro-inflammatory, or toxic conditions (Stewart et al., 2011). Ocular surface toxicity, especially to benzalkonium chloride (BAK) preservative, has been established and thoroughly discussed in the literature, which is why preservative-free treatment options are increasingly advocated, especially in patients already presenting with OSD (Stewart et al., 2011; Zhang et al., 2019). Performing a comprehensive tear film assessment in glaucoma patients may be beneficial and lead to a better understanding of the disease. To the best of our knowledge, no studies performed a full ocular surface assessment in glaucoma patients on topical treatment with IOP-lowering eye drops.

Research objectives and significance:

The main objective of the study is to investigate signs and symptoms of ocular surface disease in patients on topical glaucoma medications.

The main objective of the study is based on the following research questions:

1. What is the occurrence of signs and symptoms of ocular surface disease (OSD) in patients with primary open-angle glaucoma (POAG) who have been on treatment with IOP-lowering eye drops for at least three months?
2. Is the occurrence of signs and symptoms of OSD in patients with POAG related to added preservatives in the IOP-lowering eye drops?
3. Is the occurrence of signs and symptoms of OSD in patients with POAG modified by the active pharmacological substance in the IOP-lowering eye drops?

4. Is the occurrence of signs and symptoms of OSD in patients with POAG related to the duration of the treatment with the IOP-lowering eye drops?

Based on research questions 2-4, the following hypotheses were formulated:

1. In a sample of patients with POAG, who have been on treatment with IOP lowering eye drops for at least three months, the frequency of signs of OSD, defined as hyperosmolarity, reduced NIKBUT, ocular surface staining, or reduced Schirmer 1 test, is greater in patients that are on eye drops with preservatives compared with those that are not.
2. In a sample of patients with POAG, who have been on treatment with IOP lowering eye drops for at least three months, the frequency of symptoms of OSD, defined as OSDI index ≥ 13 or SPEED II values >5 , is greater in patients that are on eye drops with preservatives compared with those that are not.

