1. In a sample of patients with POAG who have been on treatment with IOP lowering eye drops for at least three months, the frequency of signs of OSD, defined as hyperosmolarity, reduced NIKBUT, ocular surface staining, or reduced Schirmer 1 test, is different in patients with self-reported poor compliance, defined as single dose skipped or forgotten more than once a week (Robin & Grover, 2011), compared with patients with good self-reported compliance.
2. In a sample of patients with POAG who have been on treatment with IOP lowering eye drops for at least three months, the frequency of symptoms of OSD, defined as OSDI index ≥ 13 or SPEED II values >5 , is different in patients with self-reported poor compliance, defined as single dose skipped or forgotten more than once a week, compared with patients with good self-reported compliance.

3. In a sample of patients with POAG who have been on treatment with IOP lowering eye drops for at least three months, the frequency of signs of OSD, defined as hyperosmolarity, reduced NIKBUT, ocular surface staining, or reduced Schirmer 1 test, is different in patients with self-reported poor compliance, defined as single dose skipped or forgotten more than once a week, compared with patients with good self-reported compliance, when adjusted for preservatives, pharmacological substance, and duration of treatment.
4. In a sample of patients with POAG who have been on treatment with IOP lowering eye drops for at least three months, the frequency of symptoms of OSD, defined as OSDI index ≥ 13 or SPEED II values >5 , is different in patients with self-reported poor compliance, defined as single dose skipped or forgotten more than once a week, compared with patients with good self-reported compliance, when adjusted for preservatives, pharmacological substance, and duration of treatment.

The results are expected to improve the understanding of the connection between glaucoma treatment with IOP-lowering eye drops and ocular surface disease. Acknowledgment of the problem may help to individualize treatment options for patients in agreement with personalized medicine. This could consequentially lead to the general improvement of patient life quality and treatment compliance that could also positively affect glaucoma treatment outcomes.

Study design:

This is a cross-sectional study with six months prospective data collection.

Study sample:

The target population is patients on topical treatment for POAG.

Study population:

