This study is a sub-study of an “Ocular Surface and glaucoma. A randomized study of IOP reducing eye drops versus surgical intervention” study (REK no. 253485). Invited to participate in the study are men and women between 50 and 75 years of age with early POAG, diagnosed in agreement with the European guidelines for glaucoma diagnoses and staging of the disease, with MD loss of less than 5 dB on visual fields and with a clinically significant cataract eligible for surgery, who come for a routine glaucoma follow-up examination and a presurgical assessment for cataract extraction at the ophthalmology practice of Ifocus Øyeklinikk in Haugesund, Norway, in the period between August 2021 and February 2022.

Exclusion criteria:

- Recent changes (<3 months) in the treatment with topical IOP-lowering medications (i.e., active pharmacological substance, dosage, preservatives) based on the patient medical journals.
- Use of more than one IOP-lowering eyedrops with different active pharmacological substances based on the patient medical journals.
- Self-reported OSD comorbidity defined as an autoimmune or inflammatory disease, such as Sjogren’s syndrome or Rheumatoid Arthritis (RA), or any other systemic disease that can directly affect the ocular surface.
- Conditions that may confound the results of the study:
 - Self-reported acute or chronic diseases such as connective tissue disease, clinically significant atopic disease, diabetes type 1 and 2, immunocompromised, or any other such condition.
 - Manifest corneal disease, dystrophy, or scarring based on the clinical exam.
 - Corneal ectasia based on the clinical exam.
 - Lid deformities based on the clinical exam.

- Recent intra- or extra-ocular surgery based on the patient medical journals.
- Previous refractive procedures like LASIK, LASEK, or radial keratotomy based on the patient medical journals.
- A previous corneal transplant, DSAEK, lamellar keratoplasty, or similar procedure based on the patient medical journals.

Recruitment:

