Corneal sensitivity is defined as the ability of the cornea to sense a variety of stimuli. Operationally, it is defined as the threshold for corneal surface to sense the touch of a fine nylon filament (0,12 mm) applied to the corneal apex by means of a Cochet-Bonnet Aesthesiometer (Luneau Technology Group). The length of the nylon filament can be adjusted (from 60 mm (highest sensitivity) to 5 mm (lowest sensitivity)). It is measured in millimeters and registered with one decimal on a numerical scale for the right and the left eye.

Meibomian gland dropout is defined as partial or total loss of acinar tissue of the meibomian glands and its function in the upper and lower eyelid. Operationally, meibomian gland dropout is defined as changes in the morphological appearance in the meibomian glands of the upper and the lower eyelid evaluated by means of infrared trans-illumination of the lids using an Oculus Keratograph 5M (OCULUS, Inc). Gland tissues are made visible using Meibo-Scan software and classified on the Meiboscale grading scale from a photograph taken with Oculus Keratograph 5M (Pult & Riede-Pult, 2013). It is registered in whole numbers on an ordinal scale that ranges from 0 to 4 (0=0% loss; 1= \leq 25%; 2=26%-50%; 3=51%-75%; 4= \rightarrow 75%) for the right and the left eye.

Predictor variables:

Preservative is defined as a substance or a chemical that is added to pharmaceutical drugs and other products to prevent decomposition by microbial growth or by undesirable chemical changes. Operationally, a preservative is defined as any of the following substances in the specification of the prescribed eye drops during the period of three months before inclusion into the study: Benzalkonium chloride, Polyquaternium-1, and Boric acid. The preservative is registered on a dichotomous scale where preservative=1 and no preservative=0.

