measurement is automatically stopped by the device if the patient moves or blinks. **Bulbar redness** will be measured and graded automatically and objectively by taking a picture with the Oculus Keratograph 5M. Similarly, **Tear Meniscus Height (TMH)** will be measured objectively from the picture taken with Oculus Keratograph 5M that has an integrated ruler and various magnification options. Following, **Schirmer 1 test** will be performed without anesthetics. The free end of the non-toxic calibrated filter paper will be placed in the temporal part of the lower eyelid of both eyes, and the patient will be asked to hold the eyes gently closed for 5 minutes. At the end of the 5-minute interval, the paper strips will be removed from each lower eyelid, and the amount of wetting of the paper will be noted. Slit-lamp examination of the anterior segment will be performed in order to evaluate **Ocular surface staining (OSS)**. A quantified 5 µl of 2% Fluorescein sodium will be instilled into each conjunctival sac with a micro-pipette (using a sterile tip), and then observation will be done with a slit-lamp using a yellow filter and cobalt blue light. **Meibum quality** and **Meibum expressibility** will be also evaluated during the slit lamp exam. Meibum quality will be assessed in each of the eight glands of the central third of the lower lid by applying pressure on the eyelid with a Q-tip. It will be estimated and graded on a scale from 0 to 3 for each gland: 0=clear, 1= cloudy, 2= cloudy with debris (granular), and 3= thick, like toothpaste (total score range, 0–24) (Nichols et al., 2011). **Meibum expressibility** will be assessed in the five central glands in the lower lid by applying pressure on the lid with a Q-tip. It will be estimated on a scale from 0-3 (0= all glands expressible; 1=3-4 glands expressible; 2= 1-2 glands expressible; 3=no glands expressible) according to the number of glands expressible (Nichols et al., 2011). **Cochet – Bonnet Aesthesiometer** will be used to measure corneal sensitivity. Fine nylon filament, the length of which can be adjusted (60 mm to 5 mm), will be used to apply different intensities of stimuli on the corneal surface. The shortest length of the filament that the patient reacts will be noted. **Meibomian gland dropout (Meibography)** will be measured by taking infrared photos of the upper and lower eyelid with Oculus Keratograph 5M with minimal discomfort to the patient. Gland tissues will be made visible by everting the upper and lower eyelids with a Q-tip and using Meibo-Scan. The degree of Meibomian dropout will be scored and noted for all four eyelids. Finally, **Self-reported compliance** will be examined by means of simple interview question of how often one may skip a dose (Appendix 4). Information's about age, gender, duration of the treatment, the active pharmacological substance, and the preservatives in the topical IOP-lowering medication will be collected from the patient journals.

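### Existing OSD may steer patients towards preservative-free drops, and the data that would let main hypotheses 1-2 allow for this are not collected

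*Protocol*

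**What the plan says.** The background part of the Protocol, just before the research objectives, discusses preservative toxicity and adds that "preservative-free treatment options are increasingly advocated, especially in patients already presenting with OSD". Main hypotheses 1 and 2 then predict that the frequency of OSD signs, and of OSD symptoms, "is greater in patients that are on eye drops with preservatives compared with those that are not". Neither names an adjustment. Adjustment is written only into secondary hypotheses 3-4, on compliance, which apply "when adjusted for preservatives, pharmacological substance, and duration of treatment". Preservative is a covariate there, and earlier OSD is not in the set.

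Under Study design: "This is a cross-sectional study with six months prospective data collection". Exposure is not allocated. The predictor variables define preservative as a yes/no property of "the prescribed eye drops during the period of three months before inclusion into the study".

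The exclusion criteria remove "Self-reported OSD comorbidity defined as an autoimmune or inflammatory disease", other systemic disease that can affect the ocular surface, diabetes, significant atopy, corneal disease, lid deformities, use of more than one active substance, and treatment changes within three months, including a change of preservative.

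Under Measurements, age, gender, duration of treatment, "the active pharmacological substance, and the preservatives in the topical IOP-lowering medication will be collected from the patient journals". Neither that list nor the Variables section contains OSD status before treatment or the reason for choosing the product.

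**The concern.** If clinicians follow the advice that the protocol reports, patients with a poor ocular surface are more likely to be on preservative-free drops. The two groups then differ in OSD for a reason unrelated to what the drops do. This is confounding by indication, and it works against hypotheses 1-2 because it raises OSD frequency in the group expected to have less.

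It is separate from the carry-over of earlier preserved treatment. It would be present even in patients who never used a preserved drop and whose exposure history is fully known.

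What is at stake is the answer to research question 2. A small, null or reversed difference could be taken as reassurance about preservatives when it partly reflects who was given which drop. The introduction motivates the work by a wish to understand cause and effect and to individualise treatment, so that reading is likely. An analysis plan not at hand could add age, sex, substance or duration, but it cannot adjust for something that was never recorded.

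**Working it through.** The protocol gives no effect size, power or group split for this contrast, so there is no figure to reproduce. The check is whether, and by how much, channelling can move the crude difference.

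**Inputs (all assumed).** For simplicity, each patient's current drop is the first, so the OSD that steers the choice is pre-treatment OSD.
- Share with prior OSD: π = 40%. It is varied below over 22% to 78%, the introduction's range for OSD prevalence in glaucoma, borrowed here as an assumption.
- Probability of a preservative-free drop: a with prior OSD, b without.
- Current OSD on preservative-free drops: 70% with prior OSD, 20% without (a gap of 50 points).
- True effect of preservative: +20 points in both strata, giving 90% and 40% on preserved drops.

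**Formulas.** The share with prior OSD in each group is
- preservative-free: q_F = πa / [πa + (1-π)b]
- preserved: q_P = π(1-a) / [π(1-a) + (1-π)(1-b)]

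Crude difference (preserved minus preservative-free) = 20 + 50 × (q_P - q_F) points.

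**Worked case, a = 70%, b = 30%.** q_F = 0.28/(0.28 + 0.18) = 0.609 and q_P = 0.12/(0.12 + 0.42) = 0.222. OSD on preservative-free drops = 0.609 × 70 + 0.391 × 20 = 50.4%. OSD on preserved drops = 0.222 × 90 + 0.778 × 40 = 51.1%. The difference is 0.7 points.

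| a / b | q_F | q_P | Crude difference (true +20) |
|---|---|---|---|
| 50% / 50% (no channelling) | 0.400 | 0.400 | +20 |
| 60% / 40% | 0.500 | 0.308 | +10.4 |
| 70% / 30% | 0.609 | 0.222 | +0.7 |
| 80% / 30% | 0.640 | 0.160 | -4.0 |

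**Sensitivity to the assumptions.**
- Over π from 22% to 78%, the 70%/30% case gives 0 to 5.6 points.
- If prior OSD persists less strongly (60% v 30% on preservative-free drops, a gap of 30 points) and π = 50%, the crude difference is +14 at 60%/40%, +8 at 70%/30%, +2 at 80%/20% and -4 at 90%/10%.
- With that weaker gap and π = 22% or 78%, it is +15.8, +11.3, +6.1 and -0.6 for the same four cases.

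Attenuation needs only mild channelling. Hiding or reversing the effect needs strong channelling or strong persistence of OSD.

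**Which remedy recovers the true value?** Using the 70%/30% case:
- Comparing within strata of prior OSD gives 90 - 70 = 20 and 40 - 20 = 20.
- Restricting both groups to patients without prior OSD gives 40 - 20 = 20.
- Removing all prior-OSD patients from the preservative-free group only gives 51.1 - 20 = 31.1.
- Removing only the excess channelled there (a cut from 70% to 30%, so q_F = 0.12/0.30 = 0.4 and OSD is 40%) gives 51.1 - 40 = 11.1.

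A one-sided exclusion therefore replaces one bias with another.

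**The case against.** A reader might infer that, by the protocol's own account, preservative-free drops are in fact given to OSD patients in this clinic and that the preservative-free group is enriched. The text does not support that. It says such drops are advocated, as general background, and gives no prescribing pattern for the clinic or the sample. With no channelling the bias is zero. Every figure above rests on assumptions.

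A reader might also infer that hypotheses 1-2 claim a causal effect. They do not. They state a difference in frequency, in a study declared cross-sectional, and research question 2 asks whether OSD is related to preservatives. The causal wording appears only as motivation.

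The exclusions also do real work, because they remove several causes of an OSD-prone eye and recent switches. What they leave is ordinary dry eye, and patients started on or moved to preservative-free drops more than three months earlier because of it.

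Finally, precision is poor in any case. With 30 subjects, an assumed 15 v 15 split and frequencies near 50%, the standard error is √(2 × 0.25/15) = 0.18, a 95% interval of about ±36 points. Power for 60% v 40% is about 19%. Adjustment will not make hypotheses 1-2 decisive.

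All of this stands and limits the severity. It does not answer the central point: the variable needed to detect or adjust for channelling is absent from the data to be collected, and leaving covariates to a later plan cannot supply it.

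**Conclusion.** The point holds as a possibility that the protocol raises itself and does not provide for. Existing OSD may influence the exposure group, the contrast in main hypotheses 1-2 is unadjusted, and neither pre-treatment OSD nor the reason for the product choice is recorded. The crude difference can be attenuated and, under strong channelling, hidden or reversed. On the assumed inputs a true 20 points becomes 10.4, 0.7 or -4.0. On milder inputs it becomes 14 to 16 points at 60%/40%. The documents do not allow any of these to be called the likely size. This should be fixed, because the remedy is cheap and the data sit in journals already being opened. It is not a fatal flaw.

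**What to change.** Add two items to the journal extraction under Measurements:
- (a) OSD complaints, findings or treatment noted before the first IOP-lowering drop, recorded separately from OSD arising on an earlier drop. The separation matters because OSD that arose on an earlier preserved drop may be an effect of the preservative, and adjusting for it would remove part of what is being studied.
- (b) Whether the preservative-free product was chosen because of surface complaints. This shows how much channelling occurred.

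Report hypotheses 1-2 crude and with pre-treatment OSD as a single stratum or covariate. State that both are associations and that a null or reversed crude difference is not evidence of no harm. If a restricted comparison is wanted, limit both groups to patients without pre-treatment OSD. Do not exclude channelled patients from the preservative-free group alone.

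The cost is two items for 30 patients and one covariate. Journal notes may be incomplete, and the adjusted or restricted estimate will be imprecise. Pre-treatment OSD also does not capture switches prompted by OSD that arose on an earlier drop. Those should be counted from the separate record and named as a remaining limitation.

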3. In a sample of patients with POAG, who have been on treatment with IOP lowering eye drops for at least three months, the frequency of signs of OSD, defined as hyperosmolarity, reduced NIKBUT, ocular surface staining, or reduced Schirmer 1 test is modified by the active pharmacological substance in the IOP-lowering eye drops.
4. In a sample of patients with POAG, who have been on treatment with IOP lowering eye drops for at least three months, the frequency of symptoms of OSD, defined as OSDI index ≥ 13 or SPEED II values >5 , is modified by the active pharmacological substance in the IOP-lowering eye drops.
5. In a sample of patients with POAG, who have been on treatment with IOP lowering eye drops for at least three months, the frequency of signs of OSD, defined as hyperosmolarity, reduced NIKBUT, ocular surface staining, or reduced Schirmer 1 test is related to the duration of the treatment with an IOP-lowering eye drop of a specific pharmacological category (prostaglandin analogs, beta-blocker, carbohydrase inhibitor or alfa-2-agonist).
6. In a sample of patients with POAG, who have been on treatment with IOP lowering eye drops for at least three months, the frequency of symptoms of OSD, defined as OSDI index ≥ 13 or SPEED II values >5 , is related to the duration of the treatment with an IOP-lowering eye drop of a specific pharmacological category (prostaglandin analogs, beta-blocker, carbohydrase inhibitor or alfa-2-agonist).

The secondary objective of this study is to investigate a relationship between compliance and signs and symptoms of the ocular surface disease.

The secondary objective of the study was based on the following research questions:

1. Is the occurrence of signs and symptoms of OSD in patients with POAG related to self-reported compliance to the treatment with the IOP lowering eye drops?
2. Is the occurrence of signs and symptoms of OSD in patients with POAG independently related to self-reported compliance to the treatment with the IOP lowering eye drops?

Based on these research questions, the following hypotheses were formulated:

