
Analyses:

The results of the comprehensive tear film evaluation will be recorded in the patient journal system (Infodoc Plenario) used at the Ifocus Øyeklinikk, Haugesund, Norway. The data collected with the Oculus Keratograph 5M by OCULUS, Inc. will be stored in a separate database called Oculus Patient Data Management. Once measurements are performed, data related to the study will be transferred from the patient journal to a data registration form (Appendix 4). The names of the patients will be replaced with ID numbers. All data will be transferred to and organized in a database (Excel, Microsoft Inc.). To identify empty cells or unrealistic values, an algorithm in Excel will flag the cells in question. A quality-assured version of the database will constitute the basis for statistical analyses. For variables measured on a numerical scale, these summaries will include the sample size, as well as the mean, standard deviation, median, minimum, and maximum. For variables measured on a categorical scale, summaries will provide the number and percentage of subjects who provided each score. Preliminary considerations of the data will include the investigation as to whether any transformation (i.e., logarithmic) should be applied prior to the statistical analyses. For categorical data, the sparseness of the data across categories will be considered, and the combination of categories prior to statistical analysis will be applied where deemed appropriate. For variables measured on a continuous scale, the statistical significance of the difference

between groups will be investigated using an Analysis of Variance (ANOVA) with appropriate post-hoc testing. For variables measured on an ordinal categorical scale, the Kruskal-Wallis signed-rank test will be employed. Questionnaire data will be analyzed using current standards. The statistical analyses will be performed using SPSS version 24. All statistical tests of hypotheses will employ a level of significance of $\alpha=0.05$. Odds ratios with 95% confidence intervals may also be used.

Project management and organization:

Principal investigator: [name]

Project manager: [name]

Resources, equipment, and physical facilities:

All equipment is available in the ophthalmic practice Ifocus Øyeklinikk in Haugesund, Norway, where the study will take place:

- The TearLab Osmolality System by TearLab Corporations.
- The Oculus Keratograph 5M by OCULUS, Inc.

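### Main hypotheses 3-4 (and, in mirror image, 1-2) are stated without mutual adjustment for substance and preservative, so an effect of one can be reported as, or hidden behind, the other

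*Protocol*

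**What the plan says.** In the Protocol, Research objectives and significance, main hypothesis 3 holds that the frequency of OSD signs, among them a "reduced Schirmer 1 test is modified by the active pharmacological substance in the IOP-lowering eye drops". Hypothesis 4 repeats this for symptoms. Hypotheses 1-2 compare users of preserved and preservative-free drops. None of the four mentions adjustment.

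The Analyses section chooses tests by measurement scale. For continuous variables, the difference "between groups will be investigated using an Analysis of Variance (ANOVA) with appropriate post-hoc testing". For ordinal variables, "the Kruskal-Wallis signed-rank test will be employed". It adds: "Odds ratios with 95% confidence intervals may also be used". "All statistical tests of hypotheses will employ a level of significance of" 0.05. No covariate, second factor, stratification or multivariable model is named.

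Adjustment does appear elsewhere: secondary hypotheses 3-4, on compliance, are to hold "when adjusted for preservatives, pharmacological substance, and duration of treatment".

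On preservatives the Introduction says: "Ocular surface toxicity, especially to benzalkonium chloride (BAK) preservative, has been established and thoroughly discussed in the literature". It also reports that "preservative-free treatment options are increasingly advocated, especially in patients already presenting with OSD".

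Under Predictor variables, preservative (yes/no) and substance (four classes) are both read from the specification of the prescribed drops. The Study population section excludes recent treatment changes and use of several substances. Nothing there balances preservative across substances.

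**The concern.** This is a cross-sectional sub-study of patients on whatever product routine care has prescribed. A comparison of substance groups without a preservative term therefore compares products. Its null hypothesis is that substance and preservative together give the same outcome in each group. That matches the stated hypothesis only if preserved shares are alike across substances.

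The protocol names preservative as a cause of the outcome and makes it a separate research question. It treats preservative and substance as confounders of compliance, but not of each other.

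What is at stake is whether research questions 2 and 3 get separate answers. A substance effect could be declared where only preservative matters. A real one could be missed if the gentler substance is mostly used in preserved form. In hypotheses 1-2, a substance effect could be credited to preservative in the same way.

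**Working it through.** **Inputs from the Protocol.** 30 subjects, chosen for feasibility, so there is no power figure to reproduce; four substance classes; two preservative states; significance level 0.05 (two-sided assumed, since sidedness is not stated).

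**Assumptions, because the Protocol gives no such figures.** Two substance groups of 20 and 10 patients; no true substance effect; preserved drops worsen a continuous measure by d = 0.8 to 1.0 SD, or raise a yes/no outcome from 30% to 70%.

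**Step 1: expected crude difference when substance does nothing.**

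- Continuous: (difference in preserved share) × d.
- Yes/no: (difference in preserved share) × (0.70 − 0.30).

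| Preserved shares | Continuous shift | Yes/no, crude |
|---|---|---|
| 30% vs 70% | 0.40 × 0.8 to 1.0 = 0.32 to 0.40 SD | 42% vs 58%, 16 points |
| 30% vs 80% | 0.50 × 0.8 to 1.0 = 0.40 to 0.50 SD | 42% vs 62%, 20 points |
| 20% vs 80% | 0.60 × 0.8 to 1.0 = 0.48 to 0.60 SD | 38% vs 62%, 24 points |

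Example: 0.30 × 0.70 + 0.70 × 0.30 = 0.42, and 0.70 × 0.70 + 0.30 × 0.30 = 0.58.

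**Step 2: how often the unadjusted test rejects at 0.05** (simulated, 20 vs 10, preserved counts held at the stated shares).

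| Preserved shares | ANOVA on substance, d = 0.8 / 1.0 | Fisher's exact | Uncorrected chi-square |
|---|---|---|---|
| 30% vs 70% | 9.7% / 12.5% | 5.9% | 11.5% |
| 30% vs 80% | 13.9% / 18.8% | 9.3% | 17.1% |
| 20% vs 80% | 19.6% / 25.8% | 13.9% | 22.5% |

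If each patient's preservative status is drawn at random with these probabilities, the continuous range is about 12-28%. Kruskal-Wallis behaves like ANOVA: with 15 vs 15 patients, shares of 80% vs 40% and d = 0.8, the rates are 12.1% and 12.4%. The Protocol names neither Fisher's test nor chi-square; they stand in for the yes/no frequencies in the hypotheses. At 40% vs 60% there is no material inflation.

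**Step 3: the same data with preservative in the model.** For continuous measures, the rate for substance returns to about 5%, provided preservative status does not depend on prior OSD.

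**Step 4: relaxing that proviso.** The Introduction says preservative-free drops are favoured in patients who already have OSD. When prior OSD lowers the chance of preserved drops, the adjusted rate rises to about 7-18% under one set of assumed selection strengths. It rises to 10-39% under a harsher set, with prior OSD correlated 0.8 with the outcome. If preservative has no effect, the unadjusted test stays near 5% and the adjusted one is worse. If preservative does have an effect, adjustment is usually better, but not under strong selection.

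**Step 5: masking.** Take a true substance effect of 1.0 SD and d = 0.8, with the gentler substance 80% preserved and the other 30%. The crude effect is 1.0 − 0.50 × 0.8 = 0.60 SD. Simulated power is 28% unadjusted against 59% adjusted.

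**The case against.** **The Protocol does not say one-way.** A reader might infer that it fixes a one-way ANOVA for hypotheses 3-4 and rules out adjustment. The text does not support that. The Analyses section is generic, ties no test to a numbered hypothesis, allows odds ratios, and names no multivariable method even for the compliance hypotheses that demand one. Its silence does not exclude adjustment. What stands is narrower: Kruskal-Wallis takes one grouping factor, the ANOVA is described only as a comparison between groups, and the hypotheses themselves omit the clause that the compliance hypotheses carry. An SAP faithful to that wording would take the crude comparison forward.

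**A crude comparison may be intended.** The secondary questions separate a relation from an independent relation, so hypotheses 1-4 could be read as simple associations. That is a fair reading of 1-2. It sits badly with 3-4, which say frequency is modified by the substance, and with an Introduction that seeks a cause-effect understanding to individualise treatment.

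**Adjustment is no cure.** This stands, as Step 4 shows. A reader might infer that adding preservative guarantees a 5% error rate or isolates a causal substance effect; the Introduction's account of who receives preservative-free drops undercuts both.

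**The size is assumed.** This also stands. Fisher's test at 30% vs 70% barely exceeds 5%. And 30 patients over 4 × 2 = 8 cells average 3.75 per cell, so any estimate will be imprecise.

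**Conclusion.** The point holds as a defect in how the hypotheses are stated and in how the named tests would answer them. Followed as written, the plan can credit a preservative effect to substance, or the reverse, or hide a real effect.

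Under the stated assumptions the unadjusted false-positive rate is roughly 10-28% for continuous measures and about 6-14% for yes/no outcomes with Fisher's test. All of this rests on assumed preserved shares, group sizes and a preservative effect that the Protocol does not give. With similar shares the problem largely disappears.

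The documents do not show that the study's results will be biased, or in which direction. They show only that nothing prevents it and that the available remedy is not applied to these hypotheses.

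**What to change.** - State main hypotheses 3-4 as adjusted for preservative, and 1-2 as adjusted for active substance.
- Test both from one patient-level model containing both terms: ANCOVA for continuous measures; for yes/no outcomes, penalised or exact logistic regression, or, for the substance question, a test stratified by preservative.
- Merge rarely used substances before outcomes are seen.
- Report the crude estimate beside the adjusted one, with the substance-by-preservative cross-table.
- Where a substance occurs in only one formulation, state that its effect cannot be separated from preservative.
- Describe the adjusted result as an association, and say why: preservative-free drops are favoured in patients who already have OSD.

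The cost is the wording of four hypotheses and one analysis paragraph. Both variables are already recorded, so no new data are needed.

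The statistical price is precision. For a given residual SD, the standard error of the substance effect grows by 1/√(1 − r²), where r is the correlation between substance and preservative. With 20 vs 10 patients, r = (share difference) × √(1/3 × 2/3) / √(q(1 − q)), where q is the overall preserved share. At 30% vs 70%, q = 13/30, r = 0.38 and the factor is 1.08. At 20% vs 80%, q = 12/30, r = 0.58 and the factor is 1.22. Adjustment also does not guarantee removal of bias, and can add some if preservative has no effect. That is why the crude result should stay in the report.
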